3.1.5. Dose-Limiting Toxicity

The DLT-evaluation period is the first cycle of treatment. DLTs are graded according to the National Cancer Institute's Common Terminology Criteria for Adverse Events (NCI-CTCAE), version 4.03, and defined as any of the following events during the DLT-evaluation period:

- A delay of SEA-BCMA treatment by more than 7 days due to toxicity
- Any AE \geq Grade 3, unless deemed by the SMC to be clearly unrelated to SEA-BCMA (in Parts A through D) except for the following AEs, which must meet these specified criteria to be considered a DLT:
 - Grade 4 neutropenia lasting more than 5 days

- Thrombocytopenia \geq Grade 4, or Grade 3 thrombocytopenia with clinically significant bleeding
- Anemia \geq Grade 4 unrelated to underlying disease
- Any Grade ≥ 3 tumor lysis syndrome, including associated laboratory evaluations, that is not successfully managed clinically and that does not resolve within 7 days without end organ damage
- Any \geq Grade 4 IRRs or Grade 3 IRRs that do not resolve to \leq Grade 2 within 24 hours with infusion interruption, infusion rate reduction, and/or standard supportive measures. In the event of a Grade 3 IRR in $\geq 20\%$ of subjects (ie, 2 or more in the first 10 subjects), all subsequent subjects will require premedication and/or modification of infusion approach per the recommendation of the SMC. For subjects receiving premedication, any \geq Grade 3 IRR will be considered a DLT.
- Any Grade ≥ 3 asymptomatic laboratory abnormality that does not resolve, with or without intervention, to \leq Grade 1 or the baseline grade within 72 hours
- Any treatment-related death

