3.1.6. Stopping Criteria

3.1.6.1. Enrollment Pause at the Cohort Level

If a subject's death is considered by the investigator, in consultation with the SMC, to be related to SEA-BCMA, enrollment will be paused within the applicable cohort until:

1. The case is reviewed by the investigator, the SMC, and the sponsor, and
2. The sponsor has notified applicable regulatory authorities of the outcome of the safety assessment and justification for restarting enrollment in the affected cohorts, and has received approval to resume, if required by local regulations.

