3.1.6.2. Enrollment Halt for the Entire Study

Enrollment in the entire study will be halted by the sponsor if the overall benefit-risk balance is considered unfavorable.

The study will be halted if any of the following occur:

- Rate of on-study toxic deaths unrelated to underlying disease occurring within 30 days of dose exceeds 10% (initially, 2 or more out of up to 20 subjects; then 3 or more out of up to 30 subjects; 4 or more out of up to 40 subjects; etc.)
- Rate of Grade 4 nonhematologic toxicity unrelated to underlying disease exceeds 25% (initially, 5 or more out of up to 20 subjects; then 6 or more out of up to 24 subjects; then 7 or more out of up to 28 subjects; then 8 or more out of up to 32 subjects; then 9 or more out of up to 36 subjects; 10 or more out of up to 40 subjects; etc.)
- Rate of \geq Grade 4 allergic reactions that cannot be controlled with standard treatments exceeds 15% (initially, 3 or more out of up to 20 subjects; then 4 out of up to 26 subjects; then 5 or more out of up to 33 subjects; 6 or more out of up to 40 subjects; etc.)

Stopping criteria will be continuously monitored throughout the study by the sponsor in consultation with the SMC, considering enrollment halt if the incidence and/or the severity of toxicity leads to a risk-benefit assessment that is unacceptable to the study population. The sponsor will consult the SMC to consider whether to allow subjects already receiving treatment to continue, to consider modifying the protocol to continue the trial, or to terminate the study.

If enrollment is halted due to safety concerns, enrollment can only be restarted after appropriate amendments and notifications to Regulatory Authorities, with approval to resume, if required by local regulations.

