3.1.9. Safety Monitoring Committee

The SMC will monitor safety throughout the study. The SMC is composed of the study medical monitor, study biostatistician, drug safety representative, and study site investigators. The committee is tasked with monitoring the safety of subjects in this study, through regular or ad hoc meetings that include review of data pertaining to dose-escalation decisions and treatment-emergent toxicities.

At a minimum, SMC meetings will be held during Part A (monotherapy dose-escalation) and during dose finding in Part B (intensive dosing) and Parts C and D (combination therapy) cohorts after all subjects in a safety run-in cohort have completed the DLT evaluation period. The SMC will also meet quarterly throughout the study for cumulative subject data review.

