6.11. Follow-up (every 12 weeks ±2 weeks)

Subjects who discontinue from treatment with SEA-BCMA will remain on the study for follow-up until withdrawal of consent, death, or study closure, whichever occurs first.

The first follow-up visit will occur 12 weeks (±2 weeks) from the most recent prior response evaluation. Subsequent follow-up visits will be scheduled for 12 weeks (±2 weeks) from the previous follow-up visit.

Subjects who discontinue treatment due to PD or who have initiated subsequent therapy will not be assessed for response but will be followed for survival. Subjects who discontinue treatment will continue to be assessed for response after EOT until PD or initiation of a new therapy. These subjects will be followed at this schedule until withdrawal of consent, death, or study closure, whichever occurs first.

The following assessments will be performed until disease progression or initiation of subsequent therapy; subjects will be followed for survival thereafter.

- Blood samples for local laboratory assessment (obtain until disease progression or until initiation of subsequent anticancer therapy)
 - CBC with differential
 - Serum chemistry panel
- Response assessments by local laboratory
 - SFLC
 - SPEP/immunofixation
 - UPEP/immunofixation if measurable disease in urine
 - BM aspirate and biopsy (for confirmation of CR) (to be submitted for central assessment of markers of response)
 - In cases of suspected or known plasmacytoma, plasmacytoma evaluation, per institutional standard imaging modality, should be performed every 4 cycles or to confirm a response of PR or better, or as clinically indicated to confirm PD.
- Blood sample for Modified SPEP for subjects with IgG myeloma only (to be collected only until subsequent therapy is initiated)
- Survival status and collection of first subsequent anticancer treatment information until death or study closure

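### The 25% nonhematologic halting rule counts Grade 4 only, so a toxicity that is fatal without first being recorded at Grade 4 does not add to it

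*Protocol*

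**What the plan says.** Protocol section 3.1.6.2 lists three numeric rules that halt the whole study.

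- **Deaths.** "Rate of on-study toxic deaths unrelated to underlying disease occurring within 30 days of dose exceeds 10" per cent: 2 or more in up to 20 subjects, 3 in up to 30, 4 in up to 40.
- **Nonhematologic toxicity.** "Rate of Grade 4 nonhematologic toxicity unrelated to underlying disease exceeds 25" per cent: 5 in up to 20, then 6 in 24, 7 in 28, 8 in 32, 9 in 36, 10 in 40.
- **Uncontrolled allergic reactions.** Grade 4 or higher, limit 15%. Section 1.7.1 repeats this rule and spells out *or higher*.

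The same section adds a halt on judgement: "Enrollment in the entire study will be halted by the sponsor if the overall benefit-risk balance is considered unfavorable". On timing it says: "Stopping criteria will be continuously monitored throughout the study by the sponsor in consultation with the SMC".

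Other safeguards stand nearby. Under 3.1.6.1, if a death is judged "to be related to SEA-BCMA, enrollment will be paused within the applicable cohort until" the case has been reviewed and the authorities notified. Section 3.1.5 makes "Any treatment-related death" during Cycle 1 a DLT. Section 3.1.9 says: "The SMC will also meet quarterly throughout the study for cumulative subject data review".

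Nothing else in the protocol or SAP brings Grade 5 events into the 25% count.

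**The concern.** The protocol uses the greater-or-equal sign elsewhere when it means it: in the allergic rule, and in the DLT definitions for thrombocytopenia, anemia and infusion reactions (3.1.5). Its absence from the second bullet therefore has a literal meaning. A fatal nonhematologic toxicity counts there only if the subject was also recorded at Grade 4 beforehand.

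Two things follow. First, the death count and the Grade 4 count never combine, so replacing one Grade 4 toxicity by a fatal one can turn a mandatory halt into no numeric signal. Second, the death rule stops at 30 days after a dose. Later deaths can occur on study: "Subjects who discontinue from treatment with SEA-BCMA will remain on the study for follow-up until withdrawal of consent, death, or study closure" (6.11). A late toxic death that is nonhematologic, not an uncontrolled allergic reaction, and never recorded at Grade 4 adds to none of the three counts. For such deaths the study-level response rests on case review and judgement, with no number that accumulates across cohorts.

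**Working it through.** **1. The plan's own limits.** The listed nonhematologic counts equal the smallest whole number r with r/n ≥ 0.25, that is r = ceil(0.25 × n). This gives 5, 6, 7, 8, 9 and 10 at n = 20, 24, 28, 32, 36 and 40, matching every listed pair. The listed counts are used below.

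**2. Outcomes in 20 subjects.** Up to 20 subjects the limits are constant (5 for Grade 4, 2 for deaths within 30 days) and counts only rise. Final counts below both limits therefore mean that no rule fired in any order of events. Fatal events here were not recorded at Grade 4 first.

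| Outcome | Grade 4 count, as written | Early deaths | Numeric halt as written | Count at Grade 4 or higher | Halt after fix |
|---|---|---|---|---|---|
| 5 Grade 4 | 5 | 0 | yes | 5 | yes |
| 4 Grade 4 + 1 early fatal | 4 | 1 | no | 5 | yes |
| 4 Grade 4 + 1 late fatal | 4 | 0 | no | 5 | yes |
| 3 Grade 4 + 2 late fatal | 3 | 0 | no | 5 | yes |

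*Early* means within 30 days of a dose, *late* means after that.

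**3. Chance of a halt by 40 subjects.** The documents give no toxicity rates, so every rate below is an assumption. Each subject independently has a nonfatal Grade 4 as worst grade (probability p4), an early fatal toxicity (pE), a late fatal toxicity (pL), or none of these. All fatal events are taken as nonhematologic. A share s of fatal events was already counted at Grade 4 before death. An exact recursion over the counts is checked after each subject n = 1 to 40, with limits held between the listed steps and the allergic rule not modelled.

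- As written, each subject adds 1 to the 25% count with probability p4 + s × (pE + pL).
- After the fix, that probability is p4 + pE + pL, whatever s is.
- In both, early deaths add to the death count with probability pE. A halt occurs when either count reaches its limit.

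| p4 / pE / pL | As written, s = 0 | s = 0.5 | s = 0.8 | After fix |
|---|---|---|---|---|
| 5% / 0.5% / 0.5% | 0.008 | 0.009 | 0.010 | 0.011 |
| 10% / 1% / 1% | 0.070 | 0.091 | 0.106 | 0.116 |
| 10% / 1% / 0 | 0.070 | 0.079 | 0.085 | 0.089 |
| 10% / 0 / 1% | 0.053 | 0.064 | 0.071 | 0.077 |
| 10% / 0 / 0.2% | 0.053 | 0.055 | 0.057 | 0.058 |
| 20% / 1% / 1% | 0.501 | 0.552 | 0.582 | 0.602 |

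The s = 0 column gives the largest possible effect of the wording. In the 10% / 1% / 1% row that is 0.116 − 0.070 = 0.046. Early deaths alone give 0.089 − 0.070 = 0.019, about 40% of it.

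**The case against.** The three bullets can be read as a deliberate tiering: deaths at 10%, uncontrolled allergic reactions at 15%, Grade 4 nonhematologic toxicity at 25%. A death rule 2.5 times as strict is a reason not to count deaths again under a looser one, and the sign in the allergic bullet does not prove a slip in its neighbour. This stands. The text is consistent with either intention and does not say which.

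Late related deaths also provoke action sooner than a 5-of-20 count would. One death judged related to SEA-BCMA pauses its cohort, with no time limit. This largely stands. The pause does, however, need attribution to SEA-BCMA, while the halting rules ask only that the event be unrelated to the underlying disease. Causality is judged separately for each drug (7.7.3.1), so a late death attributed only to dexamethasone or pomalidomide would meet neither the pause nor any count.

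The size is easily overstated. Section 7.7.1.1 requires changes in severity to be recorded, so some fatal events will already stand in the count at Grade 4. With weekly or two-weekly dosing, a death on treatment normally falls within 30 days of a dose, so late toxic deaths should be rare. Both points stand, which is why the table varies s and includes a 0.2% late rate.

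A reader might infer that fatal toxicity goes unmonitored. The documents do not support that: deaths within 30 days have their own stricter limit, and the pause, the committee review and the benefit-risk halt cover the rest.

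**Conclusion.** The point holds as a minor wording gap. On the literal text, a fifth severe nonhematologic toxicity in 20 subjects halts the study if it is Grade 4 but triggers no numeric rule if it is fatal and was not first recorded at Grade 4. The other safeguards narrow the gap but do not combine the two counts.

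Its size depends on assumed rates and on the share of fatal events already counted at Grade 4. At 10% Grade 4 with 1% early and 1% late fatal, the fix adds between 0.010 (80% already counted) and 0.046 (none) to the chance of a halt by 40 subjects. It would be tempting to quote the step from 0.070 to 0.116 as the effect, or to put it down to late deaths. It is an upper bound, and part of it comes from early deaths that already count under the death rule. With late deaths only, the step is at most 0.053 to 0.077 at 1%, and 0.053 to 0.058 at 0.2%.

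Nor do the documents support calling the omission an error. They show only that the wording leaves Grade 5 out and gives no reason.

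**What to change.** In the second bullet of 3.1.6.2, write *Grade 4 or higher* in place of *Grade 4*, and add that each subject counts once at worst grade. Keep all count limits, the death rule, the cohort pause and the benefit-risk halt as they are.

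This takes one phrase and one sentence in an amendment and needs no new data. After the safety reporting period only SAEs judged related to study treatment are reported (7.7.7), so deaths from subsequent therapy stay out.

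The price is a somewhat higher chance of a halt: negligible at low toxicity (0.008 to 0.011), and at most 0.50 to 0.60 at 20% Grade 4 plus 2% fatal, a total still below the 25% limit. That matters because restarting enrollment requires amendments and regulatory notification. Early toxic deaths would count under two rules, as a fatal uncontrolled allergic reaction within 30 days already does. Late fatal hematologic toxicity would still lie outside every count.

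If leaving Grade 5 out was intended, one sentence saying that fatal events count only under the death rule removes the ambiguity without changing the chance of a halt. It leaves in place the reversal shown for 20 subjects.

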3.1.7. Retreatment

Retreatment with SEA-BCMA monotherapy or with SEA-BCMA and combination therapy is permitted with medical monitor approval, for subjects who achieve clinical benefit (defined as stabilization or improvement of disease-related symptoms as assessed by the investigator) objective response (OR) (a partial response [PR] or better) on study and then experience disease progression after discontinuing initial treatment with SEA-BCMA. Eligibility criteria in Section 4.1 and Section 4.2 must be re-evaluated before initiating retreatment. Subjects who discontinue SEA-BCMA treatment due to Grade ≥ 3 toxicity are not eligible for retreatment with SEA-BCMA. The retreatment dose level for each subject will not exceed the highest safe dose level and will be determined by the medical monitor and the site investigator.

3.1.8. End of Study

The study will be closed approximately 3 years after the last subject receives the last dose, or when no subjects remain in follow-up, whichever occurs first. In addition, the sponsor may terminate the study at any time (Section 10.3.2).

3.1.9. Safety Monitoring Committee

The SMC will monitor safety throughout the study. The SMC is composed of the study medical monitor, study biostatistician, drug safety representative, and study site investigators. The committee is tasked with monitoring the safety of subjects in this study, through regular or ad hoc meetings that include review of data pertaining to dose-escalation decisions and treatment-emergent toxicities.

At a minimum, SMC meetings will be held during Part A (monotherapy dose-escalation) and during dose finding in Part B (intensive dosing) and Parts C and D (combination therapy) cohorts after all subjects in a safety run-in cohort have completed the DLT evaluation period. The SMC will also meet quarterly throughout the study for cumulative subject data review.

3.1.9.1. Part A Dose-escalation Safety Monitoring

During monotherapy dose-escalation, the SMC will review clinical data from enrolled subjects for safety assessment and for DLT determination. The SMC will make recommendations on dose level and cohort size in conjunction with the mTPI decision rules chart. A maximum of 4 subjects are allowed per cohort, with multiple cohorts allowed at each dose level (ie, the SMC

may recommend subsequent enrollment of cohorts of 1, 2, 3, or 4 subjects depending on the number of DLTs observed and cumulative data review).

In addition to determination of DLTs and dose-escalation recommendations, the SMC may make one or more of the following recommendations during the study, as applicable:

- Recommendation or requirement of a premedication regimen as prophylaxis against IRRs
- Further evaluation of safety of SEA-BCMA at a given dose
- Evaluation of alternative approaches to SEA-BCMA infusion
- Evaluation of an intermediate SEA-BCMA dose level during dose-escalation
- Evaluation of longer (eg, q4wk) SEA-BCMA dosing intervals
- Consideration of postremission dosing (not exceeding tested dose levels deemed tolerable)
- The SEA-BCMA dose and dosing interval to be evaluated in the monotherapy expansion cohort based on activity and tolerability of dose levels during escalation
- The recommended single-agent dose and schedule for SEA-BCMA based on the safety and activity data

The process for dose-escalation decisions and dose-interval recommendations, and the roles and responsibilities of the SMC will be detailed in an SMC charter.

3.1.9.2. Parts B, C, and D Safety Monitoring

During dose finding safety run-in cohorts in Parts B, C, and D, the SMC will review clinical data from enrolled subjects for safety assessment and for DLT determination. The SMC will make recommendations on the SEA-BCMA dose.

In addition to determination of DLTs and dose recommendations for the combination, the SMC may make 1 or more of the following recommendations during the study, as applicable:

- Recommendation or requirement of a premedication regimen as prophylaxis against IRRs
- Further evaluation of safety of SEA-BCMA on intensive dosing schedule and/or in combination with dexamethasone
- Evaluation of alternative approaches to SEA-BCMA infusion
- Evaluation of an intermediate SEA-BCMA dose on intensive dosing schedule and/or in combination cohorts
- Consideration of postremission dosing (not exceeding tested dose levels deemed tolerable)
- The recommended dose and schedule for SEA-BCMA on intensive dosing schedule and/or in combination based on the safety and activity data

3.2. Method of Assigning Subjects to Treatment Groups

Subject allocation to a dose level will be determined by mTPI decision rules as illustrated in [Table 2](#) and will occur upon approval of subject enrollment by Seagen or their designee.

The medical monitor will assess the safety of SEA-BCMA administration throughout the trial and, for safety reasons, may override the model's allocation of a subject to a particular dose level.

The study design allows for concurrent enrollment in multiple cohorts. If 2 or more expansion cohorts with identical eligibility criteria are open for enrollment concurrently, allocation will be determined by the sponsor or designee prior to informed consent.

3.2.1. Rationale for Selection of Doses

3.2.1.1. Monotherapy

For adult phase 1 studies of monoclonal antibodies, either body size-based dosing or fixed dosing may be considered. Based on an analysis of 12 mAbs, these 2 dosing approaches performed similarly across the mAbs in terms of their population and individual PK performances (Wang 2009). In addition, the PK variability of mAbs introduced by either dosing approach is moderate relative to the variability generally observed in pharmacodynamics, efficacy, and safety (Bai 2012). Available data from clinical trials and extensive population PK modeling of monoclonal antibodies in oncology also support use of fixed dosing for oncology indications (Hendrikx 2017). Fixed dosing could offer advantages in ease of dose preparation, and reduced chance of dosing errors. In addition, previous clinical trials of non-fucosylated and bivalent antibodies have utilized this approach during phase 1 with no significant safety concerns (Sehn 2012; Rosen 2017). Based on the predicted broad therapeutic window for SEA-BCMA, a fixed dosing strategy is used.

The monotherapy starting dose of 100 mg is based on a 1.25 mg/kg starting dose with a nominal subject weight of 80 kg. The starting dose was selected based on preclinical studies and PK/pharmacodynamic modeling and is expected to provide an adequate safety margin with the potential for clinical benefit. Data supporting the proposed starting dose include:

- Preclinical testing of SEA-BCMA in cynomolgus monkeys indicates a favorable safety profile at the proposed starting dose. The BCMA receptor in the cynomolgus monkey does not cross-react with SEA-BCMA; therefore, preclinical testing in this model is an indicator of safety in the absence of target ligation. The HNSTD in the cynomolgus monkey was 100 mg/kg for 2 doses administered at a 3 week interval. No adverse effects were observed at this dose. The proposed starting dose of 1.25 mg/kg is lower than 1/6 of the monkey HNSTD, using body surface area for animal-to-human dose conversion based on body weight, and represents an appropriately conservative starting dose.
- Human PBMCs co-cultured in vitro in the presence of BCMA-expressing myeloma cells and treated with SEA-BCMA displayed minimal cytokine activation. In PBMCs from donors with normal-affinity Fc γ RIII (representing approximately 90% of the target patient population), of 29 cytokines tested, SEA-BCMA induced a minimal change in IL-8 at 100 μ g/mL (corresponding to the C_{max} of a dose of approximately 5 mg/kg). In PBMCs from donors with high-affinity Fc γ RIII (representing approximately 10% of the target patient population), SEA-BCMA induced minimal to moderate cytokine

production. Of 29 cytokines evaluated, IL-8 and MIP-1b were the only immune activating cytokines consistently induced by treatment with 100 µg/mL of SEA-BCMA. In addition, no proliferation of myeloma cells expressing BCMA was observed when treated with 100 µg/mL of SEA-BCMA.

- SEA-BCMA is active in 7 of 7 tumor xenograft models tested, with a lowest active dose of 0.03 mg/kg in the disseminated NCI-H929 luciferase tumor xenograft model in NSG mice. In some models, repeat dosing enables ligand blocking to contribute to antitumor activity. Soluble factors, including soluble BCMA, are predicted to impact SEA-BCMA binding to target cells below 20 µg/mL of antibody, which corresponds to the predicted C_{max} of a dose of approximately 1 mg/kg.
- Based on PK simulations, the proposed dosing interval of q2wk will achieve 99% target receptor occupancy over the dosing interval after 2 doses of 400 mg assuming a serum half-life of 21 days, or 800 mg assuming a serum half-life of 11 days. Ninety-nine percent receptor occupancy is desired because ligand blocking by SEA-BCMA is one mechanism contributing to its antitumor activity, and full receptor occupancy may be required for optimal activity. Alternative dosing intervals may be explored after consultation with the SMC.

The dose-escalation design is reasonable for a monoclonal antibody in which target expression is restricted to plasmablasts and plasma cells and is anticipated to have minimal potential for toxicity to other organs and tissues. Ninety-nine percent receptor occupancy over the dosing interval is expected to induce an optimal antitumor activity. Based on PK simulations, this will be achieved at doses ranging from 400 to 1600 mg. The proposed dose-escalation plan consists of 2-fold increases per dose level, enabling efficient escalation (2 to 3 dose-escalations) into a dose range where optimal antitumor activity is anticipated to be achieved. This plan will preserve safety while avoiding exposure of an excessive number of subjects to subtherapeutic doses.

Alternative dosing strategies, including intermediate doses or longer dosing intervals, may be explored upon the recommendation of the SMC following evaluation of PK, pharmacodynamics, safety, and activity from the available clinical data.

During Part A (monotherapy dose-escalation), 6 DE subjects were treated at the highest tested dose of 1600 mg q2wk. No DLTs were observed in these 6 subjects; based upon this and cumulative safety data from prior dose cohorts, the sponsor, in consultation with the SMC, deemed 1600 mg q2wk tolerable and selected this as the monotherapy expansion dose for the standard q2wk dosing schedule.

